#### **6.3 Pharmacokinetic/Pharmacodynamic Analyses Set(s)**

##### **6.3.1 Pharmacokinetic (PK) Concentration Analysis Set**

The PK concentration analysis set consists of all subjects who have received at least one dose of efavaleukin alfa and have at least one quantifiable PK sample collected.

##### **6.3.2 Pharmacodynamic (PD) Analysis Set**

The PD analysis set consists of all subjects who have received at least one dose of investigational product and for whom at least one PD parameters have quantifiable baseline sample and at least one quantifiable post-baseline PD sample collected.

#### **6.4 Anti-drug Antibody Analysis Set**

**The Anti-drug Antibody Analysis Set is defined as the subset of subjects in the Safety Analysis Set who had at least 1 evaluable anti-drug antibody test.**

**Immunogenicity data will be analyzed according to the actual treatment received.**

### **7. Planned Analyses**

#### **7.1 DLRMs**

DLRMs: The study will have DLRMs for each cohort after the last subject in the cohort completes the DLT evaluation period. Section [3.1](#) details the timing and scope of each DLRM planned for the study. All available data for subjects up to and including the data snapshot date will be included in the analysis based on an “as-is” snapshot of the database without data locking. Data will be subject to ongoing checks for integrity,

completeness and accuracy in accordance with the Data Management Plan; however, there is no requirement to resolve outstanding data issues ahead of the DLRM snapshot. DLRM analysis will include subject-level listings and plots of available safety data (labs, and vitals) for each cohort and the BLRM analysis if required. The recommendations for dose escalation/dose modifications will be based on the DLRMs.

## **7.2 Final Analysis**

A final analysis will be performed after the end of the study, i.e., after the last subject in phase 1b part of the study completes the study (including the treatment period and safety follow-up period), or early terminates. All analyses described in Section 9 will be performed at this time. Analyses will be based on all available data.

Data will be subject to ongoing checks for integrity, completeness and accuracy in accordance with the Data Management Plan with the expectation that all outstanding data issues are resolved ahead of the final lock.

## **8. Data Screening and Acceptance**

### **8.1 General Principles**

The objective of the data screening is to assess the quantity, quality, and statistical characteristics of the data relative to the requirements of the planned analyses.

### **8.2 Data Handling and Electronic Transfer of Data**

The Amgen Global Study Operations-Data Management (GSO-DM) department will provide all data to be used in the planned analyses. The database will be subject to edit checks outlined in the Data Management Plan (DMP). See details of this section in the DMP.

### **8.3 Handling of Missing and Incomplete Data**

Subjects may be missing specific data points for a variety of causes. In general, data may be missing due to a subject's early withdrawal from study, a missed visit, or inability to evaluate an endpoint at a particular point in time. The general procedures outlined below describe what will be done when a data point is missing.

### **8.3.1 Efficacy**

No data imputation will be performed for missing efficacy endpoints.

### **8.3.2 Safety**

The following imputation for missing or incomplete data will be performed if required:

Incomplete or missing start/stop dates for adverse event and concomitant medication will be imputed as described in [Appendix A](#).

Laboratory measurements that are below the lower quantification limits will be considered equal to the lower limit of quantification for all analyses unless explicitly noted otherwise. PD data that are below the lower limit of quantification will be considered equal to half of the lower limit of quantification for all analyses unless specified otherwise. PD data that are above the upper quantification limits will be considered equal to the upper limit of quantification for all analyses unless specified otherwise.

## **8.4 Detection of Bias**

Lack of protocol compliance and the potential for biased statistical analyses will be examined by assessing the incidence of important protocol deviations in each cohort. The clinical study team will identify and document the criteria for important protocol deviations.

## **8.5 Outliers**

Outlier data will not be excluded unless scientifically justified.

PK serum concentration data will be evaluated for outliers by visual inspection and decisions to re-assay individual samples will be made in accordance with standard PKDM practices.

## **8.6 Distributional Characteristics**

Not Applicable

## **8.7 Validation of Statistical Analyses**

Programs will be developed, maintained, and output will be verified in accordance with current risk-based quality control procedures.

Tables, figures and listings will be produced with validated standard macro programs where standard macros can produce the specified outputs.

The production environment for statistical analyses consists of Amgen-supported versions of statistical analysis software, for example the SAS System.

## **9. Statistical Methods of Analysis**

### **9.1 General Considerations**

Standard descriptive statistics will be provided. All binary endpoints will be summarized using the number and percentage of subjects. All continuous endpoints will be summarized using descriptive statistics including mean, standard deviation, minimum, maximum, and number of non-missing observations (n). Summaries will be provided at all scheduled time-points unless specified otherwise. Data collected at unscheduled visits or time-points will be included in the analysis unless stated otherwise. **All safety and efficacy analyses will be performed using the Safety Analysis Set based on subject's actual treatment received.**

Only critical subject-level data listings will be provided in the clinical study report.

### **9.2 Subject Accountability**

The number and percent of subjects who are screened, enrolled, have received at least one dose of efavaleukin alfa, completed investigational product, discontinued from investigational product (including reasons for discontinuing), completed study, discontinued the study (including reasons for discontinuing) will be summarized overall and by treatment group. Separate subject disposition will be provided for the follow-up till week 52 and the extended follow-up.

Key study dates for the first subject enrolled, last subject enrolled, and last subject's end of study will be presented.

### **9.3 Important Protocol Deviations**

Important Protocol Deviations (IPDs) categories are defined by the study team before the first subject's initial visit and updated during the IPD reviews throughout the study prior to database lock. If a snapshot is taken during the study rather than a database lock at the end of the study, categories should be updated during the IPD reviews throughout the study prior to database lock. These definitions of IPD categories, sub-category codes and descriptions will be used during the course of the study. The final IPD list is used to produce the summary of IPD table and the list of subjects with IPDs. The number of subjects with important protocol deviations and protocol deviations due to COVID-19 will be summarized in a table. A list of protocol deviations for subjects impacted by COVID 19 will also be provided.

Eligibility deviations are defined in the protocol. A list of deviations from eligibility criteria will also be generated.

## **9.4 Demographic and Baseline Characteristics**

Subject demographic and baseline disease characteristics will be summarized and include the following variables:

### **9.4.1 Demographic Characteristics**

- Age (years) at screening (continuous summary statistics)
- Age categories (number and percent of subjects in 18 - 64, 65 - 74 years,  $\geq 75$  years)
- Sex (number and percentage of males and females)
- Ethnicity (number and percentage of Hispanic or Latino and Not Hispanic or Latino)
- Race (number and percentage of subjects in each race, or mixed race combination)

### **9.4.2 Baseline Characteristics**

#### **Physical Measurements**

- Height and weight (continuous summary statistics)

#### **Disease characteristics:**

- Duration of cGVHD (continuous summary statistics)
- Duration of steroid refractory cGVHD (continuous summary statistics)
- Information collected on cGVHD medical history eCRF (e.g. underlying malignancy type for which subject received HSCT, Donor type, Stem cell source etc.) (number and percentage of subjects)

- NIH- Form A-2014 assessment of each organ system (number and percentage of subjects)
- Overall cGVHD severity as marked on Chronic Graft versus Host Disease Staging Evaluation eCRF (number and percentage of subjects)

#### **Baseline immunosuppressant medication**

- **Systemic Corticosteroids**
- **mTOR inhibitors**
- **Calcineurin inhibitors**

## **9.5 Efficacy Analyses**

### **9.5.1 Analyses of Primary Efficacy Endpoint(s)**

No primary endpoint is an efficacy endpoint.

### **9.5.2 Analyses of Secondary Efficacy Endpoint(s)**

No secondary endpoint is an efficacy endpoint.

### **9.5.3                   Analyses of Exploratory Efficacy Endpoint(s)**

## **9.6                   Safety Analyses**

### **9.6.1                   Analyses of Primary Safety Endpoint(s)**

The primary endpoint is safety. The analysis will include the descriptive summary statistics for adverse events, disease-related events, laboratory test results, vital signs, and physical measurements. Details are described in respective section below.

### **9.6.2                   Adverse Events and Disease-related Events**

The Medical Dictionary for Regulatory Activities (MedDRA) version 25.0 or later will be used to code all adverse events to a system organ class and a preferred term.

The subject incidence of adverse events will be summarized for all treatment-emergent, serious treatment emergent, treatment-related, those leading to withdrawal of investigational product, fatal and of special interest (if applicable). The identification of adverse events of special interest is a continuous process. Events may be identified and documented as the safety profile of the drug. The severity of each adverse event will be graded using CTCAE version 4.03 criteria.

Subject incidence of all treatment-emergent, serious treatment emergent, treatment-related, serious treatment-related, those leading to withdrawal of investigational product or other protocol-required therapies, and fatal adverse events will be tabulated by system organ class and preferred term in descending order of frequency. Treatment emergent, serious, and treatment-related events will also be presented by preferred term and worst severity grade using CTCAE version 4.03 criteria.

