7.4.2.1.1 Phase 1b

Dose adjustment of efavaleukin alfa for individual subjects is not allowed until the [REDACTED] is determined. The Medical Monitor should be informed of withholding of efavaleukin alfa for acute clinical events such as acute infection or major surgery. Once the [REDACTED] dose is determined, all phase 1b subjects may continue study therapy at the [REDACTED] dose and frequency (at the discretion of the Sponsor, following discussion and agreement between the principal investigator and medical monitor) and will be subject to the dose adjustment guidelines in Section 7.4.2.1.2. A subject experiencing worsening of cGVHD that requires the addition of new immunosuppressive medication(s) at any time during the study or initiation of an increase in systemic corticosteroid dose above baseline after week 4 of the study (at the discretion of the treating investigator) will be deemed a treatment failure. These subjects will discontinue treatment and will have a safety follow-up visit (see Section 9.1.5).

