## **2. Objectives, Endpoints and Hypotheses**

### **2.1 Objectives and Endpoints**

Objectives	Endpoints
Primary	

• To evaluate the safety and tolerability of multiple ascending doses of efavaleukin alfa in subjects with steroid refractory chronic graft versus host disease (cGVHD)

	

• Incidence of dose limiting toxicities (DLTs) at first 4 weeks

• Incidence of all treatment-related and treatment-emergent adverse events and serious adverse events

Secondary	
Exploratory	

Objectives	Endpoints

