## **3. Study Overview**

### **3.1 Study Design**

This is an open-label, multi-center phase 1b/2 study to evaluate the safety and efficacy of efavaleukin alfa in subjects with steroid refractory cGVHD.

The phase 1b part of the study will be conducted as a multiple ascending dose (MAD) study. Each dosing cohort will consist of between 3 and 6 DLT-evaluable subjects who will receive efavaleukin alfa SC either every week (QW) or every 2 weeks (Q2W) plus protocol permitted background therapy for 52 weeks. The DLT evaluation period is defined as 4 weeks after the first dose of study IP. At the discretion of the Sponsor, following discussion and agreement between the principal investigator and medical monitor, subjects responding to efavaleukin alfa (as assessed by the end of week 50), who wish to continue treatment, may continue to receive efavaleukin alfa treatment at their current dosing regimen for up to an additional 52 weeks. The remaining subjects will complete the week 52/EOT visit. All subjects who continue to receive efavaleukin alfa during the extended dosing period will be re-evaluated at week 76 for their response to treatment. Following discussion and agreement between the principal investigator and medical monitor, the Sponsor may decide to allow these subjects to continue treatment

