through week 102 (Q2W dose) or week 103 (QW dose). Subjects participating in extended dosing will complete the week 104/end of extended treatment (EOET) visit. At the discretion of the Sponsor, following discussion and agreement between the principal investigator and medical monitor, subjects responding to efavaleukin alfa (as assessed by the end of week 104), who wish to continue treatment beyond week 104, may continue to receive efavaleukin alfa treatment at their current dosing regimen for up to an additional 156 weeks. Only subjects who are deemed eligible to continue extended dosing beyond week 102 or week 103 will complete dosing at week 104. The remaining subjects will complete the week 104/EOET visit. All subjects who continue to receive efavaleukin alfa during the extended dosing period will be re-evaluated every 6 months for their response to treatment. Following discussion and agreement between the principal investigator and medical monitor, the Sponsor may decide to allow these subjects to continue treatment through week 258 (Q2W dose) or week 259 (QW dose). Subjects participating in extended dosing through week 258 or 259 will complete the week 260/EOET visit. All subjects will complete the 6-week safety follow-up after the last dose of efavaleukin alfa.

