## **Actual Treatment Received**

---

**Actual treatment received is the IP the subject actually received regardless of the dose specified in the protocol for the cohort. In cases where a subject received multiple different efavaleukin alfa doses, the actual treatment received will be based on the highest efavaleukin alfa dose received.**

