### **Treatment Emergent AE (TEAE)**

A treatment emergent adverse event is any adverse event categorized as adverse events starting on or after first dose of investigational product as determined by "Did event start before first dose of investigational product" equal to "No" or missing on the Events eCRF and up to and including 42 days after the last dose of investigational product excluding events reported after End of Study date on eCRF form, whichever is earlier.

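### By-dose adverse event percentages have no common follow-up window, so they can mix dose with time at risk; cohort 5 events after the dose reduction count under the higher dose

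*SAP*

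**What the plan says.** The second primary endpoint in SAP 2.1 is "Incidence of all treatment-related and treatment-emergent adverse events and serious adverse events". The DLT endpoint beside it is fixed at 4 weeks; this one has no common horizon.

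- **Measure (SAP 9.6.2):** "Subject incidence of all treatment-emergent, serious treatment emergent, treatment-related, serious treatment-related, those leading to withdrawal of investigational product" and related categories, by system organ class and preferred term.
- **Window (SAP 5.5, TEAE):** from first dose "up to and including 42 days after the last dose of investigational product", or to the End of Study date if that comes first.
- **Grouping (SAP 9.1 and 5.1):** "All safety and efficacy analyses will be performed using the Safety Analysis Set" by actual treatment received. For a subject given several doses, "the actual treatment received will be based on the highest efavaleukin alfa dose received".
- **Who continues (SAP 3.1):** "subjects responding to efavaleukin alfa (as assessed by the end of week 50), who wish to continue treatment, may continue" for up to 52 more weeks. After week 104 responders again "may continue to receive efavaleukin alfa treatment at their current dosing regimen for up to an additional 156 weeks".
- **Who stops early:** subjects deemed treatment failures (Protocol 7.4.2.1.1): "These subjects will discontinue treatment and will have a safety follow-up visit". A DLT also ends study therapy (SAP 5.5).
- **Cohort 5 (SAP 3.1 and 5.3):** enrolment at the planned dose was discontinued and ongoing subjects moved to a lower dose. The SAP defines a Planned Treatment Period, which for cohort 5 ends the day before the first reduced dose, and a Dose Reduction Period from that dose onwards.
- **Week-52 cuts elsewhere:** disposition (SAP 9.2) and corticosteroid reduction (SAP 9.6.9).
- **Exposure:** days on product and total dose are summarised (SAP 9.6.8; by dose level in Protocol 10.4.2.3.8).

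**The concern.** A crude percentage of subjects with an event rises with the length of observation. Here that length is set partly by response and tolerability, both of which may differ by dose. A dose level with many responders accumulates events over a second year or longer; one with many treatment failures is observed for a few months. A difference between columns can then reflect dose, time at risk, or selection of responders, and the percentages alone cannot separate these.

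Cohort 5 adds a second mixture. Under the highest-dose rule, an event that starts on the reduced dose is counted in the higher-dose column. That column describes a dose sequence under a single-dose label.

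At stake is how the tolerability of ascending doses is read, which is the primary objective. No hypothesis test is planned (SAP 2.2), so this is a matter of interpretation, not of type I error.

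**Working it through.** **1. The plan's own figure.** SAP 3.2 gives an 87% (40 subjects) or 79% (30 subjects) chance of seeing an event with 5% incidence. 1 − 0.95^40 = 87.1% and 1 − 0.95^30 = 78.5%. Both reproduce. They treat incidence as one number with no reference to exposure time.

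**2. Nominal windows.** The study day of week n is 7n + 1 (schedule tables, SAP Appendix G); add 42 days.

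| Last dose (Q2W / QW) | Window, days |
|---|---|
| Week 50 / 51 | 351 + 42 = 393 / 358 + 42 = 400 |
| Week 102 / 103 | 715 + 42 = 757 / 722 + 42 = 764 |
| Week 258 / 259 | 1807 + 42 = 1849 / 1814 + 42 = 1856 |

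The first extension multiplies the window by 757/393 = 1.9 and the full one by 1849/393 = 4.7. The longest windows are protocol maxima, and early termination may have prevented them. A last dose at week 16 gives 113 + 42 = 155 days.

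**3. Effect on percentages.** The documents give no event rates or exposure by cohort, so everything from here is illustration. Assume constant rates of 0.3 (lower dose) and 0.6 per year (higher dose), with p = 1 − exp(−rate × days/365.25).

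- Common 52 weeks (364 days): 25.8% vs 45.0%.
- Half the lower dose continues to 764 days, higher dose at 400 days: (28.0% + 46.6%)/2 = 37.3% vs 48.2%. The gap shrinks and the order is kept.
- Half the higher dose continues instead: 28.0% vs (48.2% + 71.5%)/2 = 59.8%. The gap widens.
- Half the lower dose continues, higher dose observed for only 224 days (about 32 weeks): 37.3% vs 30.8%. The order reverses.

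**4. How far the reversal depends on assumptions.**

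- Against 400 days it never occurs: even if every lower-dose subject continues, the result is 46.6% vs 48.2%.
- Against 224 days it needs a continuing share above (30.79 − 28.00)/(46.61 − 28.00) = 15%, and roughly constant rates.
- Suppose half the 52-week hazard falls in the first 12 weeks and the later rate then persists. The lower dose has 52-week hazard 0.299: half of it (0.1495) early, and 0.1495/280 per day after day 84. This gives 27.3% at 400 days and 40.1% at 764 days, mean 33.7%. The higher dose (0.598) at 224 days has 0.299 + 0.299 × 140/280 = 0.4485, or 36.1%. There is no reversal.

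**5. What a 52-week table gains.** With 6 subjects per dose and the constant rates of step 3, the chance that the lower dose shows more affected subjects in the 224-day scenario is 0.48. A crude 52-week table lowers it to 0.30 (25.8% vs 30.8%). It would be 0.15 only if everyone were observed for all 52 weeks. The cut removes the extension effect but not the early-stopping effect.

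**6. Cohort 5.** Assume a 393-day window, 0.6 per year before the reduction and 0.3 after, with the reduction at day d: p = 1 − exp(−[0.6d + 0.3(393 − d)]/365.25).

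| Reduction at week | Reported under higher dose | Event before reduction | Share with first event after reduction |
|---|---|---|---|
| 8 (d = 56) | 30.8% | 8.8% | 72% |
| 16 (d = 112) | 34.0% | 16.8% | 51% |
| 26 (d = 182) | 37.6% | 25.8% | 31% |

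Without a reduction the figure would be 47.6%.

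**The case against.** The strongest reply is that little depends on these tables. They are descriptive and no between-dose test is specified. Dose decisions used the 4-week DLT window and the review meetings' access to all safety data, and the expansion cohort and phase 2 are cancelled. Days on product are summarised and disposition is split at week 52, so a reader with at most about six subjects per cohort can see unequal follow-up. All of this stands, and it limits the weight of the point. It does not show which events fell in which period, and neither summary corrects the percentages.

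The highest-dose rule can also be defended as conservative, since an event soon after a reduction may still stem from the higher dose. That stands too and belongs in a footnote to any split.

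A reader might infer three stronger things that the documents do not support:

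- That the endpoint has no window. It has one per subject, capped at End of Study; only a common horizon is missing.
- That the crude tables will make a higher dose look safer. Step 4 shows that this needs a short higher-dose window and roughly constant hazards. The two serious hypersensitivity reactions in Protocol 3.2.3 came within 24 hours of the first dose, and early-onset events like these are little affected.
- That the SAP overlooks the cohort 5 dose change or plans no split. It defines both periods. Parts of the analysis sections are redacted, so non-use can be claimed only for the readable text of 9.6.2.

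**Conclusion.** The point holds as a cheap improvement to reporting. By-dose percentages for the TEAE/SAE endpoint can mix dose with outcome-dependent time at risk, and the cohort 5 column combines two doses. Both follow from the window, the grouping rule and the continuation rules, without any assumed rate. The size and direction are unknown because exposure by cohort and the timing of the reduction are not given. The illustrations show that a true difference can be shrunk, widened or, under strong assumptions, reversed. The 4-week DLT endpoint is unaffected.

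**What to change.** Keep the crude tables. Add to SAP 9.6.2, by dose level:

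1. Overall TEAE, SAE and treatment-related subject incidence limited to the first 52 weeks from first dose, with the number still under observation and median days at risk beside it. Show later events separately, labelled as data in selected responders.
2. For cohort 5, the same overall summary split by the Planned Treatment Period and the Dose Reduction Period, with days at risk in each and a footnote that events early in the second period may reflect carry-over from the higher dose.

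Kaplan-Meier or exposure-adjusted estimates are optional. With so few subjects they add little precision, censoring at treatment failure may be informative, and exposure-adjusted rates suit events concentrated at the first doses poorly.

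The cost is some SAP wording and a few tables from dates already collected. Precision stays poor at 3 to 6 subjects per cohort: 2 of 6 has an exact 95% interval of 4% to 78%. The cohort 5 periods may be short. Early stopping still affects the 52-week figure, which is why numbers observed and days at risk must stand beside it.
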